#### **7.3.2. Interim Analysis**

No interim analysis is planned for this study.

Statistical Analysis Plan  
Protocol No.: Fontem-PK-01

## **8. STATISTICAL ANALYSES**

### **8.1. SUBJECT DISPOSITION AND WITHDRAWALS**

A disposition table will summarize the number of subjects screened, screen failed, randomized, Safety Population, Outcomes Population, PK Subpopulation, completed the study, discontinued early, and reasons for discontinuation. Percentages will be based on the Safety Population.

The reason for discontinuation will be summarized using the categories specified in the case report form (CRF) page.

Subjects excluded from the Outcomes Population and PK Subpopulation will be listed.

### **8.2. PROTOCOL DEVIATIONS**

All deviations related to safety, informed consent, eligibility, and protocol compliance will be listed by subject.

### **8.3. DEMOGRAPHICS AND BASELINE CHARACTERISTICS**

Demographics (age, sex, race, ethnicity, body weight, height, body mass index [BMI]) and baseline characteristics (heart rate, systolic and diastolic blood pressure, and eCO results) will be summarized descriptively.

### **8.4. MEDICAL HISTORY**

Abnormalities identified from any physical examinations at the Screening visit, if required by the study physician, will be recorded in the CRF as Medical History. Any medical conditions with a start time prior to first use of study product will be recorded as part of the subject's medical history.

Medical history data will be coded with MedDRA Version 22.0 or later and will be listed by System Organ Class (SOC) and Preferred Term (PT).

### **8.5. TOBACCO/NICOTINE PRODUCT USE HISTORY AND FTND**

Results from the Nicotine Use History Questionnaire will be summarized descriptively for each question.

Fagerström Test for Nicotine Dependence (FTND) responses will be summarized descriptively for each question. In addition, the total score will be calculated and included in the summary. Total FTND score will be the total of the scores to each question as follows:

### Fagerstrom Test for Nicotine Dependence

PLEASE TICK {✓} ONE BOX FOR EACH QUESTION			
How soon after waking do you smoke your first cigarette?	Within 5 minutes		3
	6-30 minutes		2
	31-60 minutes		1
	After 60 minutes		0
Do you find it difficult to refrain from smoking in places where it is forbidden? e.g. Church, Library, etc.	Yes		1
	No		0
Which cigarette would you hate to give up?	The first in the morning		1
	Any other		0
How many cigarettes a day do you smoke?	10 or less		0
	11 - 20		1
	21 - 30		2
	31 or more		3
Do you smoke more frequently in the morning?	Yes		1
	No		0
Do you smoke even if you are sick in bed most of the day?	Yes		1
	No		0
Total Score			
SCORE	1- 2 = low dependence 3-4 = low to mod dependence	5 - 7= moderate dependence 8 + = high dependence	

### 8.6. PRIOR AND CONCOMITANT MEDICATIONS

Prior and concomitant medications will be listed, and prior medications will be flagged.

### 8.7. SUBJECTIVE MEASURES

Response to product liking, urge to smoke, and intent to use product again questionnaires are recorded as VAS scores or Likert scales and will be treated as continuous variables.

The PES is considered as a 7-point scale. Responses will be presented as the following factor scores:

- Satisfaction: average of the response scores from Questions 1, 2, 3, and 12;
- Psychological reward: average of the response scores from Questions 4 to 8;
- Aversion: average of the response scores from Questions 9, 10, 16, and 18;
- Relief: average of Questions 11, 13, 14, 15, and reversed for Questions 20 (i.e., not at all = 7, extremely = 1);
- Questions 17, 19, & 21 will be summarized as individual item scores.

Statistical Analysis Plan  
Protocol No.: Fontem-PK-01

For the Urge to Smoke questionnaire, the maximum response (Emax), defined as the maximum absolute value of change from baseline and time to maximum response (TEmax) will be determined. In the case of multiple values considered as Emax, the earliest time point associated will be used in calculating TEmax.

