9.14.6.1 Urge to Smoke Questionnaire

The Urge to Smoke questionnaire (Appendix 13.2.4) will be administered at the same time points when there is a blood draw for nicotine PK; i.e., at -5, 3, 5, 7, 10, 15, 20, 30, 45, 60, 90, 120, 135 (or 15 minutes into *ad lib* session), 150 (or 30 minutes into *ad lib* session), 165 (or 45 minutes into *ad lib* session), and 180 (or 60 minutes into *ad lib* session) minutes relative to the first puff of the cigarette/ENDS at that visit during Visits 2 to 7.

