10.3.2 Subjective Effects Measures

Where applicable, responses to the questionnaires recorded as VAS scores or Likert scales will be treated as continuous variables and summarized descriptively by study product and time point for each questionnaire item using means, standard deviations (SD), medians, and ranges.

The PES will be considered as a 7-point scale. Responses will be presented as the following factor scores:

- a) Satisfaction: average of the response scores from Questions 1, 2, 3, and 12;
- b) Psychological reward: average of the response scores from Questions 4 to 8;
- c) Aversion: average of the response scores from Questions 9, 10, 16, and 18;
- d) Relief: average of Questions 11, 13, 14, 15, and reversed for Question 20 (i.e., not at all = 7, extremely = 1);
- e) Questions 17, 19, 21 will be summarized as individual item scores.

The maximum response (E_{max}) and time to maximum response (TE_{max}) will be determined for the Urge to Smoke questionnaire.

Responses and parameters will be listed by subject and summarized by study product using descriptive statistics.

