## **7. GENERAL STATISTICAL CONSIDERATIONS AND DEFINITIONS**

### **7.1. BASELINE AND VISIT WINDOWS**

Unless otherwise specified in this section, baseline, which is defined as the last non-missing assessment prior to the first product use within a visit, will be used in baseline and change from baseline analyses. Baseline adjustment will be performed by subtraction of the baseline nicotine concentration from each nicotine concentration obtained after test product use on that day for each subject.

The summary tables by visit will use the values from the scheduled visit.

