### **7.3. DATA HANDLING RULES**

#### **7.3.1. Missing Data**

Missing data will not be imputed. Where individual data points are missing because of dropouts or other reasons, the data will be considered missing at random and summarized based on reduced denominators.

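### SAP 8.7's earliest-time tie rule gives a visit with no change in urge to smoke (Emax = 0) the shortest available TEmax instead of leaving TEmax undefined

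*SAP*

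**What the plan says.** - **Parameters.** Protocol 10.3.2 says that Emax and TEmax "will be determined for the Urge to Smoke questionnaire". It gives no tie rule and no rule for a visit without a response.
- **Emax.** SAP 8.7 makes it absolute: "defined as the maximum absolute value of change from baseline and time to maximum response (TEmax) will be determined". No minimum or non-zero change is required.
- **Ties.** SAP 8.7: "In the case of multiple values considered as Emax, the earliest time point associated will be used in calculating TEmax".
- **Baseline.** SAP 7.1: "baseline, which is defined as the last non-missing assessment prior to the first product use within a visit". For the urge score this is the −5 minute value.
- **Schedule.** Protocol 9.14.6.1 lists "i.e., at -5, 3, 5, 7, 10, 15, 20, 30, 45, 60, 90, 120, 135", then 150, 165 and 180 minutes. After baseline there are 15 scores, the first at 3 minutes.
- **Missing data.** SAP 7.3.1: "Missing data will not be imputed". Nothing there sets a derived time to missing when there was no change.
- **Reporting.** Protocol 10.3.2 lists the parameters by subject and summarizes them by product. SAP 7.2 gives mean, median, SD, minimum and maximum for continuous variables.

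**The concern.** A time to maximum response has meaning only if there was a response. The tie rule is sensible when a real maximum is reached more than once, since the first occasion is the natural time to report. When Emax is zero the same rule picks a time from a set in which nothing happened, and always picks the earliest.

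The resulting number is therefore wrong, and it lies at the short end of the scale. A visit with no change ranks ahead of one with a large change a few minutes later. The Urge to Smoke questionnaire is listed among the primary endpoints in both documents, and TEmax is one of two parameters derived from it. At stake are the mean and minimum TEmax reported for each product.

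**Working it through.** The plan states no figure to reproduce. The check applies SAP 8.7 literally and then works out the effect on a product's mean.

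**Rule.** Emax = max over t of |urge(t) − urge(−5)|, with t running over the 15 post-use times. TEmax = the earliest t at which that maximum occurs.

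**Single visits** (scores invented for illustration, scale taken as 0 to 100):

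| Profile | Emax | TEmax (min) |
|---|---|---|
| Baseline 0, all later scores 0 | 0 | 3 |
| Baseline 50, all later scores 50 | 0 | 3 |
| Baseline 100, all later scores 100 | 0 | 3 |
| Baseline 80, lowest score 20 at 10 minutes | 60 | 10 |
| Baseline 80, all later scores 80 except 79 at 165 minutes | 1 | 165 |

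The first three rows show the artefact: 15 zero changes, 15 ties, and the earliest time returned. The fourth shows a real 60-unit response ranked as slower than no response. The fifth shows how narrow the trigger is, because one unit of change at one time removes it.

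**Effect on a product mean.** Inputs: n = 20 (Protocol 10.1, SAP 6), one visit per product per subject, and k flat visits scored at 3 minutes. The other 20 − k visits have mean TEmax m, which the documents do not give and which is assumed here.

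- Mean with flat visits included = [3k + (20 − k)m]/20.
- Mean with flat visits set to missing = m.
- Reduction caused by the rule = k(m − 3)/20.

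| Assumed m (min) | k = 1 | k = 2 |
|---|---|---|
| 7 | (7 − 3)/20 = 0.2 | 0.4 |
| 15 | (15 − 3)/20 = 0.6 | 1.2 |
| 150 | (150 − 3)/20 = 7.35 | 14.7 |

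**Other summaries.** The minimum becomes 3 whatever the other visits show. With all other visits at one common value, the median did not move for 1, 2 or 4 flat visits out of 20. With spread-out values it could shift slightly.

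**Missing early scores.** Flatness is needed only at observed times. Protocol 9.14.6 lets the blood draw take precedence over the urge score. If the 3-minute score is missing, the flat visit takes the next observed time instead.

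**The case against.** The strongest reply is that this will seldom happen and changes little when it does. The score is a mark on a paper VAS, treated as continuous, and must equal baseline at every observed time over three hours. Subjects smoke at least 10 cigarettes a day and arrive after 12 hours without nicotine, so a visit fixed at the bottom of the scale is unlikely. One fixed at the top must survive 10 puffs and then an hour of unrestricted use. TEmax is not tested; the only planned test is on Cmax and AUC over 0 to 120 minutes. The same visit contributes Emax = 0 to the Emax summary, and the pair would show in the subject listings. All of this stands and keeps the point minor. It does not make 3 minutes a correct value.

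A reader might infer more in three ways, none of which the documents support.

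- **That the rule makes an ineffective product look fast in the product comparison.** This needs flat visits to be frequent, and more so on some products. The documents give no frequency. They also do not say that TEmax will be read as speed of relief; under absolute change it can equally mark a rise in urge.
- **That a flat visit always ranks as the single fastest, at 3 minutes.** The value may be shared with subjects whose change truly peaks then, and it is later if the first score is missing. If TEmax were derived separately for the ad libitum hour, which the SAP does not state, it would be 135 minutes.
- **That the problem is larger because the protocol's abbreviation list defines Emax as a reduction.** SAP 2 says that its analyses supersede the protocol's high-level plan, and SAP 8.7 uses absolute change. The mismatch needs reconciling, but it does not enlarge this point under the SAP as written.

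**Conclusion.** The point holds as a minor defect in a derivation rule. Read literally, SAP 8.7 returns a definite but meaningless TEmax for any visit with Emax = 0, and nothing elsewhere in either document prevents it. This follows from the text without assumptions.

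Its size does rest on assumptions. Per flat visit, the mean falls by 0.2 to 7.35 minutes for typical TEmax values from 7 to 150 minutes. The upper figure applies only if most subjects reach their largest change in the ad libitum hour. With no flat visits, which is quite possible, the effect is nil. No planned hypothesis test is affected.

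**What to change.** Add to SAP 8.7:

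- TEmax is not defined, and is set to missing, when Emax = 0.
- The earliest-time rule applies only when Emax > 0.
- The number of visits with Emax = 0 is reported by product beside the TEmax summary.

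This fits the SAP's absolute-change definition, under which Emax cannot be negative and no direction of response is defined. If Emax is instead reconciled to the protocol's reduction definition, the condition should become Emax not greater than 0. A visit in which urge only rises would otherwise be mishandled in the same way. For example, with baseline 80, a score of 82 at 3 minutes and a climb to 93 at 180 minutes, the largest reduction is 80 − 82 = −2, at 3 minutes.

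The cost is a short addition to the SAP and one condition in the program. TEmax would be summarized on slightly fewer visits, so it describes only visits with some change. Reporting the count keeps the others in view.

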## 8.8. PUFF TOPOGRAPHY

Puff duration, volume, peak flow, and average flow rate will be summarized by study product.

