9.14 Product Use Sessions (Visits 2 to 7)

9.14.1 Defined Product Use Session

During Visits 2 to 7, subjects will undergo a product use session in which they take 10 puffs from their usual brand of combustible cigarette (Visit 2 only) or 10 puffs from their randomly allocated blu disposable e-cigarette. The beginning of each puff will be separated by a period of 30 seconds. For each puff, subjects will be instructed to achieve a puff duration of at least 1 second. Blood samples will be taken for nicotine PK analysis (Section 9.14.3).

9.14.2 *Ad libitum* Product Use Session

During Visits 2 to 7, subjects will undergo an additional product use session during which they use the cigarette (Visit 2 only) or blu disposable e-cigarettes *ad libitum*, i.e., by taking as many and as frequent puffs as they desire. Subjects may use as many cigarettes and e-cigarettes as they would like. During this session, puffing topography measurements will be made using the CReSS Pocket device (Section 9.14.4), and blood samples will be taken for PK analysis (Section 9.14.3).

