10.3.3 Puff Topography

The following topography parameters will be assessed:

- Puff duration
- Puff volume
- Peak puff flow rate
- Average puff flow rate
- Inter-puff interval

Summary statistics of puff topography parameters will be presented, including means, SD, medians, and ranges.

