## **2. INTRODUCTION TO THE STATISTICAL ANALYSIS PLAN**

This statistical analysis plan (SAP) is based on Study Fontem-PK-01 ‘Nicotine uptake and abuse liability assessments of 5 blu disposable electronic cigarettes in comparison to a combustible cigarette,’ original version, dated 13 July 2021. It details the methodology to be used in analyzing the data and outlines the specifications in the Tables, Figures, and Listings (TFLs) for data to be included for executing the final statistical analyses for this study.

The analyses specified in this document supersede the high-level analysis plan described in the protocol. Study measurements and assessments, planned statistical methods, and critical derived variables are summarized in this plan. Planned tables, figures and listings are specified.

The final pharmacokinetic (PK) and statistical analysis will proceed according to the SAP approved by Fontem US LLC as well as Xyzagen Inc. and CPAN Inc. Any deviations in final analyses from this SAP will be documented in the clinical study report (CSR).

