#### **3.2.2. Secondary Objectives**

- To compare puff topography when subjects smoke a combustible cigarette versus use of the blu disposable e-cigarette.
- To evaluate overall safety in subjects using the blu disposable e-cigarette.

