#### **3.3.2. Secondary Endpoints**

- Puff topography (e.g., count, duration, volume, flow rate, and inter-puff interval)

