## **9. CHANGES TO THE PLANNED ANALYSES**

None.

Statistical Analysis Plan  
Protocol No.: Fontem-PK-01

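### SAP 8.8 drops inter-puff interval without declaring it and plans no summary of puff count, so the topography comparison does not cover how many puffs were taken or how they were spaced

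*SAP*

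**What the plan says.** The secondary objective in both documents is worded "To compare puff topography when subjects smoke a combustible cigarette versus use of the blu disposable e-cigarette" (SAP 3.2.2; the same in Protocol 2.1). The matching endpoint, again the same in both, is "Puff topography (e.g., count, duration, volume, flow rate, and inter-puff interval" (SAP 3.3.2, Protocol 2.2).

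The two analysis sections differ. Protocol 10.3.3 lists five parameters: puff duration, puff volume, peak flow rate, average flow rate and "Inter-puff interval". It then says "Summary statistics of puff topography parameters will be presented, including means, SD, medians, and ranges". SAP 8.8 reads in full "Puff duration, volume, peak flow, and average flow rate will be summarized by study product".

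On precedence, SAP 2 states "The analyses specified in this document supersede the high-level analysis plan described in the protocol". SAP 9, headed "CHANGES TO THE PLANNED ANALYSES", reports none.

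Topography is measured only in the second session of each visit (Protocol 9.14.4). Subjects then use the product "by taking as many and as frequent puffs as they desire" (Protocol 9.14.2). In the first session they take 10 puffs with 30 seconds between puff starts (Protocol 9.14.1).

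**The concern.** Because the SAP supersedes the protocol's plan, the inter-puff interval line in Protocol 10.3.3 does not fill the gap in SAP 8.8. A programmer following the SAP would produce topography tables for duration, volume and flow only. Those tables would describe the puffs themselves, but not how many there were or how far apart they came. If either feature were added later, SAP 2 would require it to be documented in the study report as a deviation, so it would no longer be a prespecified result.

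SAP 8.8 also leaves two smaller things open. It does not say how the many puffs in a session become one value per subject and product. And by-product means and SDs allow a side-by-side description, but they do not give the precision of a within-subject difference, because they leave out the correlation between a subject's cigarette and e-cigarette values.

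**Working it through.** **Step 1: set the lists side by side.**

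| Feature | Endpoint (Protocol 2.2, SAP 3.3.2) | Protocol 10.3.3 | SAP 8.8 |
|---|---|---|---|
| Puff count | yes | no | no |
| Duration | yes | yes | yes |
| Volume | yes | yes (puff volume) | yes (not stated to be per puff) |
| Flow rate | yes | yes (peak, average) | yes (peak, average) |
| Inter-puff interval | yes | yes | **no** |

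SAP 8.8 keeps 4 of the 5 parameters in Protocol 10.3.3 and covers 3 of the 5 features in the endpoint list. SAP 9 does not record the one dropped parameter.

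**Step 2: look for a substitute elsewhere in the SAP.**

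- Mass change (SAP 8.10.1) is kept separate by session but exists for e-cigarettes only.
- The number of cigarettes and e-cigarettes used in the ad libitum session is recorded (Protocol 7.3). SAP 5.2 mentions product use in general, but no SAP section names a summary of this number.
- The 120–180 minute nicotine parameters and the two session ratios use the −5 minute baseline (SAP 8.9), so their ad libitum part still carries nicotine from the defined session.
- SAP 7.2 says data are generally listed by subject. A listing is not a summary.

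**Step 3: why inter-puff interval needs a definition common to all products.** This illustration rests on assumptions and does not measure the defect. Assume each cigarette is smoked as in the defined session (10 puffs 30 s apart, so 9 × 30 s = 270 s, the protocol's 4.5 minutes), and that k cigarettes are spread over the 3,600 s.

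- Mean over all gaps = 3600/(10k − 1). This gives 3600/19 = 189.5 s for k = 2, 3600/29 = 124.1 s for k = 3 and 3600/39 = 92.3 s for k = 4.
- With an assumed gap g between cigarettes, the mean = (270k + (k − 1)g)/(10k − 1). For g = 300 s this is 44.2, 48.6 and 50.8 s; for g = 600 s it is 60.0, 69.3 and 73.8 s.
- Mean within a cigarette = 30 s throughout.
- Median over all gaps = 30 s throughout, because 18 of 19, 27 of 29 and 36 of 39 gaps are 30 s.

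So if gaps between cigarettes were excluded while pauses within a single e-cigarette were kept, the same puffing pattern would score 30 s on one product and 44 to 190 s on the other. A per-subject median over all intervals avoids this under the assumed pattern.

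**Step 4: what by-product SDs leave open.** For a paired difference with n = 20, equal SDs and within-subject correlation ρ, the 95% half-width is 2.093 × √(2(1 − ρ)/20) SD. Assuming ρ = 0 gives 0.66 SD and assuming ρ = 0.8 gives 0.30 SD. The documents give no value of ρ, so this shows only that the by-product table cannot supply the precision.

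**The case against.** The endpoint list opens with e.g., so it is illustrative. Puff count is also missing from Protocol 10.3.3, so the SAP did not drop it. A reader might infer that the SAP removed two committed parameters; the documents support that for inter-puff interval only. For puff count, the fault is a named example of the endpoint with no planned analysis.

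A reader might also infer that number and spacing are the only things free in the ad libitum session. The synopsis says that session has no restrictions, so duration, volume and flow are free too. What sets count and spacing apart is that the defined session fixes them.

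It may be argued that Protocol 10 lets the SAP modify the plan. It does, and it requires an amendment only for major changes to primary endpoints or their analysis. Topography is secondary, so no amendment is missing. That permission does not make the statement in SAP 9 correct.

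Finally, both documents treat topography descriptively, there is no power calculation, and a side-by-side summary can serve an objective worded as a comparison. This stands: the paired difference is an improvement, separate from the omission. Neither document plans to relate ad libitum nicotine to the quantity puffed, so the case does not rest on such an analysis.

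**Conclusion.** The point holds as a gap in a secondary analysis and an incorrect declaration of no changes. One of five parameters in Protocol 10.3.3 is dropped undeclared, and two of five illustrative endpoint features have no SAP summary. This follows from the text alone and needs no assumption.

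Two stronger readings are not supported. First, the documents do not show that the data would go uncollected: topography is measured by device and data are generally to be listed. Second, saying that no measure of quantity common to both product types is summarized holds only if volume means volume per puff, as Protocol 10.3.3 suggests and SAP 8.8 does not state. The interval and half-width figures above depend on assumed use patterns and correlations. They show why definitions and pairing matter, not how large the defect is.

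**What to change.** Revise SAP 8.8 as follows.

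1. Add ad libitum puff count and inter-puff interval by product. Summarize the recorded number of cigarettes and e-cigarettes used in that session.
2. Use one value per subject per product: the session total for count, and the subject's mean or median over puffs, chosen in advance, for the other parameters. State that volume is per puff. Define inter-puff interval identically for cigarettes and e-cigarettes, for example as the per-subject median of all intervals in the session, or with one common cut-off for long pauses applied to every product. State whether it runs start-to-start or end-to-start. Do not exclude gaps for cigarettes only. Besides the bias, that could need per-cigarette times, and Protocol 7.3 records start and stop times per use episode without saying that an episode is one cigarette.
3. Since each subject is scheduled to use all six products, report the paired e-cigarette-minus-cigarette difference with a 95% interval. Label it descriptive, unadjusted for multiplicity and confounded with visit order, because the cigarette is always used at Visit 2 and only Visits 3 to 7 are randomized.
4. Correct SAP 9 accordingly. If inter-puff interval is to stay out, record and justify that there.

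The cost is a SAP revision and a few table rows, with no amendment. The downside is more unadjusted intervals. Six topography parameters by five e-cigarettes gives 30, of which 30 × 0.05 = 1.5 would be expected to exclude zero by chance if there were no true differences; hence the descriptive label.
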